## 1. Study general information

**Study Title:** Pilot study to assess patients and health workers needs involved in Sickle Cell Disease management

**Sponsor Name:** Not applicable.

**Summary:**

This pilot research aims at assessing the needs of patients and health workers involved in Sickle Cell Disease (SCD) management in Nigeria. To achieve this, a mixed methodology will be adopted and the research design to be adopted for this study will be case study. Data for this study will be collected using triangulation methods. A simple random and purposive sampling techniques will be used to select respondents for the study. The collected data for this study will be presented and analysed using SPSS and thematic analysis.

The primary objective of this study is to understand the needs of SCD patients and health workers involved in SCD management.

## 2. Background and rationale

Sickle cell disease (SCD) is a public health problem globally and presents major challenges to our health care systems. SCD is an inherited blood disorder caused by abnormal haemoglobin (Grosse, et al., 2011). Currently, approximately 250 million people worldwide carry the gene responsible for SCD and other haemoglobin disorders. Each year about 400,000 infants are born with a major haemoglobin disease worldwide. In Nigeria, the prevalence of SCD is 20-30/1000 live births annually (Ademola, 2015; WHO, 2006). SCD is associated with complications and most patients experience both chronic and episodic pain, and acute pain crisis is the most common reason for the emergency department use by patients with SCD (King et al., 2014).

Problems associated with SCD and complications have been adopted from different perspectives: genetic counseling, knowledge and awareness, pharmacological treatment like hydroxyurea, Patient and Physician Relationship, caregivers perspectives on the SCD treatment, socio-economic perspectives, etc (Galadanci, 2014; Ademola 2015; Green, et al., 2016; Makani et al., 2015; McGann, et al., 2015). However, while these perspectives have helped to better understand the problems, few studies are reported in literature to assess the needs of patients and in our knowledge none of them has been conducted in the centres concerned by this study.

## 3. Objectives

### 3.1. Primary objective

To assess the needs of SCD patients and health workers, with particular reference to the disease management in the clinical centre.

The study is intended as a pilot experience to verify the feasibility of the action through a structured survey. This is a descriptive, mixed method prospective questionnaire-based study. The study is intended as a pilot experience to verify the feasibility of the action through a structured survey.

### 3.2. Sample size determination

As pilot experience, the questionnaires will be administered to 30 SCD patients or parents/legally designated representatives of children affected by SCD and 30 Professionals working with SCD patients (mainly doctors and nurses) in each centre for a total of 120 patients and 120 health workers. A focus group discussion will be run with the SCD patients/parents. Following the pilot study, a wider survey will be launched involve patients, parents and healthcare professionals in the whole country and in other centres involved in the project.

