### 3.3. Setting

The study will be conducted in the following four centres: Barau Dikko Teaching Hospital Kaduna State University (BDTH), Ahmadu Bello University Teaching Hospital Zaria (ABUTH), National Hospital Abuja (NHA), and Federal Medical Centre Katsina (FMC).

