### 3.4. Sampling strategy

Random and purposive sampling technique.

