## 4. Inclusion and exclusion criteria

The following inclusion criteria will apply for patients/parents:

- Aged  $\geq 18$
- Have SCD diagnosis or having a child with a SCD diagnosis
- Attending the centre from at least 6 months
- Nigerian nationality
- Informed Consent signed

The following inclusion criteria will apply for healthcare professionals:

- Working in a SCD clinic
- At least 5 years of experience with SCD patients
- Informed Consent signed

The following exclusion criteria will apply for all participants:

- Informed consent form withdrawal
- Illiterate subjects
- Any psychiatric conditions impairing the participation in this study.

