## 5. Study procedure

### 5.1. Questionnaire completion

After obtaining the informed consent, subjects (patients, parents/legally designated representatives and healthcare professionals) will be asked to complete the questionnaire. Two questionnaires have been developed, one addressed to patients, parents, legally designated representatives (Annex I) and another one for healthcare professionals (Annex II)

The following measures will be adopted to reduce the interviewer effect:

- The investigator will give instructions to complete, but questionnaires will be self-completed.
- Participants will have time to complete the questionnaire in a private setting.
- Completed questionnaires will be blindly deposited in a closed box. This will be thus safeguarded by the investigators.
- Completed questionnaires will be returned to the coordinating investigator for analysis.

Questionnaires will be pseudonymised: an alphanumeric code will be indicated on each questionnaire and reported on the corresponding informed consent form.

All the study investigators are researchers/officers in the centres not involved in patients' clinical management. The veracity and consistency of responses are of paramount importance for the

---

validity of the study and the improvement of the management of SCD patients: all the actions necessary to allow the participants to freely express themselves will be adopted.

Together with the questionnaire, participants will receive information about the time and venue for the focus group discussion (Annex III). For those who are willing, reminders about the focus group will be sent by e-mail/phone.

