### SECTION B

- 1. If you are a patient, what is your diagnosis? If you are a parent, what is the diagnosis of your child?**
  - A. Sickle cell disease [ ]
  - B. Sickle cell/b-thal [ ]
  - C. Sickle Beta-Plus Thalassemia [ ]
  - D. Other (please specify) \_\_\_\_\_
- 2. How is your/your child current transfusion regime?**
  - A. I am not transfused [ ]
  - B. I am regularly transfused [ ]
  - C. I am occasionally transfused [ ]
  - D. Other (please specify) \_\_\_\_\_
- 3. Where do you usually get information about Sickle Cell Disease?**
  - A. Websites
  - B. Social Networks
  - C. Scientific journals
  - D. TV
  - E. Radio
  - F. Leaflets/booklets
  - G. Doctor/nurse
  - H. Other patients
  - I. Relatives/friends
  - J. Religious leaders
  - K. Other (please specify) \_\_\_\_\_

---

**4. Please, indicate your main information source:** \_\_\_\_\_

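### The 120 patients in Section 3.2 are patient-side respondents in any mix of patients and parents/representatives, and Annex I does not record which is which

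*Protocol*

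**What the plan says.** Section 3.2 defines the patient-side sample in each centre as follows: "the questionnaires will be administered to 30 SCD patients or parents/legally designated representatives of children affected by SCD". With 30 professionals added, it gives the size as 30 of each "in each centre for a total of 120 patients and 120 health workers". Section 3.3 fixes the number of centres: "The study will be conducted in the following four centres".

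Nothing else in the protocol fixes how many of the 30 should be patients. Section 3.4 reads in full: "Random and purposive sampling technique". Section 4 requires respondents to be at least 18 and admits either role: "Have SCD diagnosis or having a child with a SCD diagnosis". A child with SCD can therefore enter only through an adult who answers for the child.

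Section 5.1 provides one questionnaire, Annex I, for patients, parents and representatives alike. Section A of that form asks for state, local government, clinic, age, gender, education and occupation. It does not ask for role. Section B opens with "If you are a patient, what is your diagnosis? If you are a parent, what is the diagnosis of your child", and the answers offered are diagnoses only.

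The primary objective in Section 3.1 is to assess the needs of SCD patients and health workers, "with particular reference to the disease management in the clinical centre".

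**The concern.** The stated size and the stated sampling unit do not match. A centre could fill its 30 places entirely with parents, or entirely with adult patients, and comply with the protocol either way. A later report of 120 patients could then describe far fewer people who have the disease.

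The missing role item makes this more than a matter of labelling. Several Annex I questions mean different things for the two roles: support received at diagnosis (7), involvement in decisions (8), instruction on pain control (9) and current health (27). An adult patient answers these from personal experience, while a parent reports on a child. If the form does not show who answered, the pooled percentages reflect an unknown blend, and a reader cannot tell whose needs they describe.

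**Working it through.** **1. The plan's own figure.** Inputs: 30 patient-side respondents per centre (Section 3.2) and 4 centres (Section 3.3). 30 × 4 = 120. The total reproduces as a count of respondents, so there is no arithmetic error.

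**2. Patients among the 120.** No section sets a minimum or maximum for either role. Each centre may have 0 to 30 patients, so the study may have 0 to 120.

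**3. Whether role can be recovered from the form.** Section A has no role item. Section B question 1 addresses both roles but stores only a diagnosis. Age gives at most a hint, because every respondent is an adult. Under Section 5.1 the questionnaire carries a code that also appears on the consent form. That route would work only if the consent record shows role, and the protocol does not say that it does.

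**4. What an unknown mix can do.** The protocol gives no response rates, so the following rates are assumptions. Let *w* be the share of adult patients. The expected percentage is *w* × p(patient) + (1 − *w*) × p(parent). The gap between two mixes is (*w*₁ − *w*₂) × [p(patient) − p(parent)].

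Pooled result, with 50% of patients and 20% of parents dissatisfied:
- all parents (*w* = 0): 20%
- 30 patients and 90 parents (*w* = 0.25): 0.125 + 0.15 = 27.5%
- 90 patients and 30 parents (*w* = 0.75): 0.375 + 0.05 = 42.5%
- all patients (*w* = 1): 50%

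Gap between two centres of 30 giving identical care:

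| Patients/parents in the two centres | Roles differ by 20 points | Roles differ by 30 points |
|---|---|---|
| 20/10 and 10/20 | 6.7 | 10 |
| 24/6 and 6/24 | 12 | 18 |
| 30/0 and 0/30 | 20 | 30 |

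**5. Scale of sampling error.** The Wilson 95% half-width at 50% is 1.96 / [2 × √(n + 1.96²)]. This gives 16.8 points at n=30, 12.3 at n=60 and 8.8 at n=120. For a difference between two centres of 30, the half-width is 1.96 × √[p₁(1 − p₁)/30 + p₂(1 − p₂)/30]. This is 25.3 points if both rates are 50%, and 1.96 × √(0.25/30 + 0.16/30) = 22.9 points at rates of 50% and 20%. These treat respondents as a simple random sample, which the partly purposive sampling does not guarantee, so they serve only for scale.

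**6. Comparison.** In the centre table, only complete separation with a 30-point role difference (30 points) exceeds the error of a difference (22.9). In the pooled result, moving from 30 to 90 patients shifts the figure by 15 points, against a half-width of about 9.

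**The case against.** The label can be read as shorthand. The same sentence in Section 3.2 names both roles, Sections 4 and 5.1 name them again, and nobody following the protocol would recruit the wrong people or the wrong number. That is fair as regards recruitment. It does not help whoever reads the results, because nothing on the form shows how many patients there were.

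A second objection is that reporting by type belongs in an analysis plan, which is not at hand. That holds for the choice of tables. But Annex I fixes what is collected, and an analysis plan cannot split answers by a role that was not recorded.

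Third, many items rate the same clinic's waiting times, laboratory, nursing and access, where the two roles may well agree. A mix reflecting who attends may also be a legitimate target for a descriptive pilot. Both points stand. The protocol offers no evidence on the size of any role difference.

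A reader might go further and infer that differences between centres will be artefacts of respondent mix, or that equal quotas are needed. The protocol does not support either. It plans no comparison between centres and describes no centre as serving only children or only adults, and a gap as large as 30 points needs total separation under assumed rates. Setting that gap against the 17-point half-width of a single centre would also be the wrong yardstick. A quota of 15 and 15 would leave per-centre cells with half-widths of about 23 points (26 at n=10), and pooled figures would no longer reflect each clinic's own mix.

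**Conclusion.** The point holds as a mismatch between label and design, made worse by a gap in the instrument. The design delivers 120 patient-side respondents, of whom 0 to 120 are patients, and Annex I cannot reliably show which. This follows from the text without any assumption.

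Its effect on results is conditional. It requires patients and parents to answer differently, and every percentage shown above rests on assumed rates. Under those rates the pooled result is the more exposed: a plausible change in mix moves it by more than its sampling error. The centre-level effect is a caution for anyone who reads the results by centre, since no such analysis is stated. This should be corrected before the forms are used, but it does not put the study as a whole in doubt.

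**What to change.** - **Section 3.2:** replace the label of 120 patients with 120 patient-side respondents (adult patients or parents/representatives).
- **Annex I, Section A:** add one tick-box item for role: patient, parent or representative.
- **Reporting:** give results for patients and for parents/representatives separately as well as pooled, and state the number of each type per centre.
- **Optional:** keep a tally by type during recruitment, aiming to include both wherever a centre serves both. A fixed quota is not required. The tally has some value because a role item cannot supply answers from a type that a centre never recruited.

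The cost is one extra item on the form and a wording change, with no additional respondents. Estimates by type are less precise: about 12 points at n=60 if the split happens to be even, against about 9 for the pooled 120, and wider still for the smaller group if it is uneven.

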**Is there any additional aspect you would like to propose to improve the management of SCD?**

---

---

---

---

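### The pilot is meant to verify feasibility, but section 3.2 commits to the wider survey without a feasibility measure or a step to revise the forms, and no respondent is asked how the questionnaire worked

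*Protocol*

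**What the plan says.** Section 3.1 states the primary objective as "To assess the needs of SCD patients and health workers, with particular reference to the disease management in the clinical centre". It then says, twice, "The study is intended as a pilot experience to verify the feasibility of the action through a structured survey".

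Section 3.2 sets the size: "the questionnaires will be administered to 30 SCD patients or parents/legally designated representatives of children affected by SCD", and the same number of professionals, "in each centre for a total of 120 patients and 120 health workers". The next step is put without a condition: "Following the pilot study, a wider survey will be launched", nationally and in other project centres.

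Section 5.1 has the forms self-completed in private and dropped in a closed box. Section 5.3 has the answers transcribed to an Excel file. Section 5.4 names SPSS and thematic analysis. Section 6 lists the start and end of data collection and the final report, with no decision or revision point.

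The open item that closes the patient form (Annex I) is "Is there any additional aspect you would like to propose to improve the management of SCD". The health-worker form (Annex II) closes by asking what would improve the respondent's work. The focus group guide (Annex III) covers health workers, services, facilities and needs. The focus group is for patients and parents only.

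**The concern.** A pilot that is to verify feasibility needs something to be measured and a point at which the result can change what follows. The protocol has neither. It names no feasibility measure such as return, completeness or completion time. It also has no step between the pilot and the wider survey at which a poor item would be reworded.

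The forms themselves collect nothing on how they worked. Self-completion in private is a sensible guard against interviewer effects, but it also means that nobody sees where a respondent hesitates or guesses. Health workers have no focus group, so their form is their only channel.

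At stake is what the pilot can say at its end. It can describe needs, but its statement on feasibility would rest on no stated measure. Items that produce plausible but wrong answers could go undetected, both in the pilot's own needs results and in any later survey that uses them.

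**Working it through.** **1. The plan's own figure.** 30 per group per centre (section 3.2) × 4 centres (section 3.3: "The study will be conducted in the following four centres") = 120 per group. This reproduces. No test or power calculation is stated, and a descriptive pilot needs none.

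**2. Failures that leave a trace.** The protocol gives no item failure rates, so I assume a range. If a proportion p of respondents leave an item blank or unusable, the chance of at least one such form among n is 1 − (1 − p)^n.

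| p (assumed) | n = 30 (one centre) | n = 120 (one group) |
|---|---|---|
| 2% | 1 − 0.98^30 = 0.455 | 1 − 0.98^120 = 0.912 |
| 5% | 1 − 0.95^30 = 0.785 | 1 − 0.95^120 = 0.998 |
| 10% | 1 − 0.90^30 = 0.958 | 1 − 0.90^120 > 0.999 |

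Failures of this kind would therefore probably be visible in the transcribed data. What is missing is a plan to tabulate and act on them. The same figures apply to an added line asking which questions were unclear, if everyone affected says so. The planned sample is thus large enough and needs no extra recruitment.

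**3. Failures that leave no trace.** For these the chance of detection from the returned forms alone is nil, whatever n is. The annexes contain items where this can happen:
- Annex II Q15 puts *Very Dissatisfied* third and the neutral option last. The other satisfaction items on that form (Q5, Q10, Q13, Q14) put the neutral option third and *Very Dissatisfied* last. Someone ticking by position gives a valid-looking wrong answer.
- Annex I Q26 runs from definite no to probable no, then definite yes before probable yes, so its options are not in order.
- Annex I Q23 has no distance below 5 km or above 70 km and no free-text option.
- Annex I Q27 goes from *Very poor* straight to the neutral option.
- Annex I Q25 asks for satisfaction with psychological support and has no option for those who answered no to Q24.

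**4. Precision for return.** For an illustrative return of 96 of 120 (80%), the Wilson 95% interval with z = 1.96 has
- centre (0.80 + 1.96²/240) / (1 + 1.96²/120) = 0.791
- half-width 1.96 × √(0.80 × 0.20/120 + 1.96²/(4 × 120²)) / (1 + 1.96²/120) = 0.071

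This gives 72% to 86%. The same 80% in one centre (24 of 30) gives 63% to 90%. Return is therefore better reported per group, pooled over centres.

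**5. Why a simple pass mark would misfire.** Suppose at least 24 of 30 were required in each of the 2 × 4 = 8 cells of group by centre. With independent returns at a true rate of 80%, one cell passes with probability P(X ≥ 24 | 30, 0.80) = 0.607, and all eight with 0.607^8 = 0.018. At 85% the joint figure is 0.27, and at 90% it is 0.81.

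A flat limit on blanks, say 10%, also fails, because some items are rightly left blank:
- Annex I Q22 has no box for no.
- Annex I Q23 applies only after a yes.
- Annex I Q25 depends on Q24.
- The reasons list after Annex II Q17 is for those who are not satisfied.

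**The case against.** The best case for the protocol has four parts.

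- **The forms already carry information.** Completed questionnaires are transcribed, and many items have a write-in option. Blanks, double ticks and write-ins will show which items fail in those ways. This stands. A reader might infer that the pilot cannot show which questions failed; step 2 shows that this goes too far. Only the untraced failures of step 3 remain hidden.
- **Silence is not commitment.** A reader might infer that the wider survey goes ahead whatever the pilot shows. Section 3.2 states an intended sequence. It sets no rule that could change the launch, but it does not say that results will be disregarded. It also does not say that the same two forms will be reused unchanged, so it cannot be claimed that faulty items will pass into the national survey.
- **The primary objective is needs assessment.** That can be met without a go/stop rule, and section 3.1 does not define the action whose feasibility is to be verified. This stands in part. A pilot followed by a wider survey makes the survey the natural reading, and feasibility is stated as the study's purpose twice.
- **A statistical analysis plan might hold feasibility summaries.** It might, and none is at hand. But the launch wording and the annexed forms belong to the protocol, and an analysis plan cannot recover answers to questions that were never asked.

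**Conclusion.** The point holds in a limited form. The protocol names feasibility as the pilot's purpose, yet it commits to the wider survey without a feasibility measure or a questionnaire-revision step, and it collects no respondent feedback on the forms.

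The loss is confined to items that are misread or force-ticked. Traced failures at 5% or more would almost certainly appear at least once in 120 forms, although the protocol does not say that anyone will look for them. One appearance is a prompt for review, not in itself grounds for rewording.

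The failure rates and the 80% return are my assumptions. The detection figures for an added feedback line also assume that those affected report it. This should be changed, since the remedy is cheap, but it does not undermine the descriptive needs assessment as a whole.

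**What to change.** 1. **Annexes I and II.** Add two closing lines to each form: *Minutes taken: __* and *Numbers of any questions that were hard to understand or had no answer that fits you: __*.
2. **Section 3.2.** State that the wider survey will be launched after per-item blanks, invalid multiple ticks and these flags have been reviewed and failing items reworded. Report return per group, pooled over centres, with its 95% interval.
3. **Conditional items.** Assess Annex I Q22, Q23 and Q25 and the reasons list after Annex II Q17 only among those to whom they apply. For Q22 this requires adding a box for no, because a blank cannot now be told from a respondent who does not need to travel.
4. **Thresholds.** If a go/stop threshold is wanted, the investigators should set it before the first questionnaire is given out. A pass mark of 24 of 30 in every cell, or an unqualified 10% limit on blanks, should not be used, for the reasons in step 5 of the working.

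The cost is two extra lines per form, one box, a short addition to 3.2, and possibly a short delay to the wider survey while items are reworded. No extra participants are needed.
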